6.3 Intervention Fidelity and Assessment of Compliance

Low adherence rates to exercises, risedronate, and CaD would impact fidelity of intervention components and limit generalizability of study results.

According to Bandura, adherence is related to "task and barrier self-efficacy". Task self-efficacy is subject's confidence in their ability to perform interventions such as exercises, and barrier self-efficacy is subjects confidence in their ability to overcome barriers to interventions. We will promote task and barrier self-efficacy through subject education, goal setting, reducing barriers, and by providing graphic feedback on goal achievements.

Feedback sheets will be provided to subjects to demonstrate progress over time in adherence to interventions, 1RM measures, weight loads for exercises, and BMD. Scripts will be provided for assisting with goal-setting and reducing barriers to promote standardization across sites. Strategies for reducing barriers to adherence to exercises will be tailored to subjects based on their scores on the Barriers Interference instrument.

6.4 Study Schedule

6.4.1 Prescreening

Potential subjects will be asked to respond to questions on the screening criteria form and Physical Activity Readiness Questionnaire (PARQ) either over the phone or electronically via our study website (see Form 1. Calendar Card Instructions *Form 13. Prescreening Questionnaire.Web_Revised*; *Form 14. Prescreening Qurestionnaire.Verbal_Revised* see *Protocol 20. Prescreening script*). Use *Protocol 21. Prescreening Procedure* to guide this process. If potential subjects meet initial inclusion criteria, they will be mailed a packet of information including: current consent forms, *Form 15. One Page Study Summary_3*, *Form 16. What to Expect at your DXA*, *Form 17. Directions to CUMC*; for printing purposes

use [Packet 1. Block Scheduled Screening Participant](#). Upon review of these forms, the potential subject will be scheduled to meet face to face to complete the Screening Consent Form at either the Creighton Osteoporosis Research Center or at UNMC (see [Protocol 22. Steps to Take Prior to Screening Visit](#)).

6.4.2 Screening Visit

Reference [Protocol 23. Block Screening Meeting](#) and section below to conduct visit.

To print the forms needed for completion of a screening visit, print [Packet 2. Screening Visit](#).

1. Participant arrives or ORC and is directed to waiting room for HOPS study.
2. Immediately upon arrival, look in Screening Binder to identify the individual's ID# and assigned RPC. Mark the participant's folder and [Form 18. Screening Visit Checklist](#) with ID#, and use highlighter to mark folder tab with assigned RPC's color.
3. Step 1: Completion of Screening Consent
 - a. RPC or Investigator greets the participant and reviews the consent form according to screening checklist and protocol (see [Form 19. Screening Consent](#); see [Form 18. Screening Visit Checklist](#))
 - b. Screener signs Screening Consent form indicating informed consent. RPC or Investigator will sign as well.
 - i. If participant decides they do not want to participate they are thanked for their time and may leave.
4. Step 2: DXA
 - a. HOPS personnel will walk participant down to ORC and let staff know that the participant is ready for their DXA.
 - b. Hand [Form 18. Screening Visit Checklist](#) to participant or staff member. ORC staff will gather height, weight, and waist circumference while the participant is in the ORC completing their DXA and they will record this data on our Checklist.
 - c. ORC personnel will complete DXA scan and record total Hip and lumber spine BMD, T-scores.
 - d. While participant is completing DXA, double check that all pages of the consent have been initialed (including signature page and last page!) and make a photocopy using the copy machine in the ORC.
 - i. We keep the original document. Place the copy in a folder for the participant.
 - e. After the DXA, the ORC personnel will direct participant back to the HOPS waiting room.
 - f. Once results of DXA are generated ORC personnel will bring results of DXA to HOPS personnel
 - i. ORC will provide an original and a copy. Place the copy in the participant's folder and the original in our folder.
5. Step 3: Questionnaires
 - a. When the participant is completing the DXA, personnel should open RedCap on the Ipad and assign an ID# according to the [Protocol 24. RedCap Data Entry](#)
 - b. After returning from their DXA, the participant will complete the following questionnaires in RedCap according to the protocol on data entry: [Form 20](#).

Osteoporosis Knowledge Test Revised (*must be 1st questionnaire), *Form 21. Demographic Profile*, *Form 22. FRAX*, *Form 23. Screening Participants Contact Information Form* *_Revised*, *Form 24. Human Activity Profile Test (HAP)* and *Form 25. International Physical Activity Questionnaire (IPAQ)*(see *Protocol 25. Administering Osteo Knowledge Test* ; *Protocol 26. Administering FRAX*; *Protocol 27. Administering HAP Questionnaire*; *Protocol 28. Administering IPAQ*

6. Step 4: Reporting DXA Results

- a. Using the *Form 26. Bone Mineral Density Report*, report DXA results to participant.
 - i. *If DXA results indicate that the participant has either normal bone density, or that they are osteoporotic*, inform participant that they do not qualify for HOPS
 - E. Provide *Form 27. Calcium FAQ*, *Form 28. Vitamin D FAQ*, and *Form 29. Osteoporosis Pamphlet*
 - F. If the screener is osteoporotic, HOPS personnel can refer them to a provider for follow up using the *Protocol 29. Referral for Osteoporotic Screeners*.
 - G. Provide a flyer or two and ask participant to help spread the word about HOPS to friends and family.
 - H. The participant is now finished and may leave.
- b. *If the DXA shows that she has low bone mass (T score between-1 and -2.49), but not yet osteoporosis (T score < -2.5)*, the screening subject will be informed that they qualify for the next stage of screening, which includes a blood draw and blood pressure check.
- c. Confirm that screener wants to proceed with the next stage of screening and complete tasks outlined in #7: Step 5, immediately below.

7. Step 5: Blood Draw, BP, and concluding visit:

- a. *If the screener needs to have their blood drawn at the CRC*:
 - i. Take blood pressure using *Protocol 30. Checking Resting Blood Pressure* as a guide. Record results on Checklist.
 - ii. Discuss an approximate date/time for blood draw so that we know when to expect communication from the CRC.
 - iii. Hand them the following forms: *Form 30. CRC Qualification*, *Form 31. CRC Directions with Map*, *Form 32. Further Questions Contact Sheet* *_Revised* and *Form 29. Osteoporosis Pamphlet*
 - iv. Inform participant that we will contact them once we receive the results of their lab work, and at that point, will send a letter to their provider regarding participation in HOPS (see *Form 33. Provider Permission Letter* *_4*).
 - v. Allow participant to leave.
 - vi. HOPS personnel should proceed with ordering blood draw by following the appropriate scenario in *Protocol 31. Ordering Blood Draw*
- b. *If the screener has blood drawn on site at the Creighton ORC*:
 - i. Take blood pressure using *Protocol 30. Checking Resting Blood Pressure* as a guide. Record results on Checklist.
 - ii. Blood draw performed by either [name] or [name]

E. [name] and [name] are trained to perform phlebotomy and transport specimens, and will follow *Protocol 32. Blood Draw Procedure*, and *Protocol 33. Blood Transportation Protocol*, when performing venipuncture, labeling tubes, and transporting back to the TNMC lab

- iii. If participant has questions or concerns about participation in HOPS, provide the *Form 32. Further Questions Contact Sheet_Revised* and *Form 29. Osteoporosis Pamphlet*, and advise that they contact one of the PIs before their enrollment visit
- iv. Inform participant that we will contact them once we receive the results of their lab work, and at that point, will send a letter to their provider regarding participation in HOPS (see *Form 33. Provider Permission Letter_4*).

6.4.3 After Screening Visit

If the screener was not qualified, follow the *Protocol 34. Steps to Take After Screening Visit* to complete follow up paperwork.

If the screener has qualified, the following tasks need completed after the screening consent visit:

1. An order for analysis of the sample will need to be placed in One Chart immediately after the screening visit (or during screening consent visit, if personnel are able to remote in to their desktop). Use *Protocol 35. Ordering Blood Tests in One Chart and Enrolling Participant*. *****An order needs to be placed before any specimens are taken to the lab.**
2. HOPS personnel will take one SST (gold top), one PST (green top), and one purple top tube to the TNMC lab. Personnel will keep one SST (gold top) tube and take it up to the lab to centrifuge and aliquot for storage (see *Protocol 36. Blood Handling Procedure* and *Protocol 37. Serum NTx and Alkphase B Aliquot and Storage*).
 - a. The following analyses will be performed using screening participants' blood sample: CBC, serum vitamin D, serum calcium, serum creatinine, parathyroid hormone (PTH), follicle-stimulating hormone (FSH) if needed, and subjects diagnosed with a thyroid condition will also have a Thyroid Stimulating Hormone (TSH) test.
 - b. At a later date, we will perform analysis of AlkphaseB, Serum NTx, and other soluble factors that may impact bone health (TBD), using the serum from the SST tube stored in [name] -80 freezer.
3. Immediately following this, or on the next business day, HOPS personnel should follow *Protocol 34. Steps to Take After Screening Visit* to complete and/or initiate the remaining items that need completed for screening purposes, including verifying RedCap data, checking lab results, calculating FRAX, etc.
4. If screening subjects remain eligible to participate after undergoing the steps listed above, study personnel will contact the individual's health care provider to request permission for the screening subject to participate in the Heartland Osteoporosis Prevention study (see *Form 33. Provider Permission Letter_4*; see *Protocol 38. Sending Provider Permission Letter*)
5. If permission is granted by the health care provider, the screening subject will be invited to enroll in the main study. The RPC schedules the participant for a time to come go to the ORC to fill out their main study consent, their PQCT, baseline questionnaires, and baseline education.

6.4.4 Enrollment/Baseline

To print the forms needed for an enrollment visit, see *Packet 3. Enrollment Visit Forms*. All other forms needed for this visit are in RedCap. Checklists for this visit are printed and available at the ORC.

1. Complete process of informed consent to the Main Study (see *Form 34. Main Study Consent*; see *Protocol 39. Main Study Consent Guidelines for Completion*.)
2. Randomization: Open the next envelope (envelope on the “top” of the pile located in desk in HOPS office at ORC) and read treatment group out loud.
3. Select the appropriate checklist (see *Form 35. Enrollment Checklist Exercise*, *Form 36. Enrollment Checklist Control*, *Form 37. Enrollment Checklist Risedronate*)
4. Participant will complete *Form 43. NOF Calcium Intake Estimate_Revised* using paper and pencil (see *Protocol 40. NOF Calcium Intake Calculator*)
5. Walk the participant down to the ORC, where they will complete the PQCT. Leave study Checklist with the participant, so that the ORC personnel can initial that the Pqct has been completed. This scan takes approximately 5 minutes.
6. During pQCT:
 1. Open RedCap complete the ID# assignment using *Protocol 24. RedCap Data Entry* (see also *Packet 4. Control Group_All Enrollment Forms*, *Packet 5. Risedronate Group_All Enrollment Forms*, *Packet 6. Exercise Group_All Enrollment Forms*, if you are using hard copy questionnaires).
 2. Locate appropriate Participant Manual (see *Packet 7. Control Group_Participant Manual*, *Packet 8. Risedronate Group_Participant Manual*, *Packet 9. Exercise Group_Participant Manual*). These are located in the ORC, although personnel will need to print copies of these periodically.

Control Group Protocol:

1. Participant Manual will contain the following:
 - a. *Form 15. One Page Study Summary_3*
 - b. *Form 38. What is Osteoporosis*
 - c. *Form 39. Exercise and Your Bones*
 - d. *Form 40. Instructions for Calcium and Vitamin D*
 - e. *Form 1. Calendar Card Instructions*
 - f. *Form 41. Lexicomp Online Patient Education Cholecalciferol*
 - g. *Form 42. Lexicomp Online Patient Education Calcium Citrate*
2. Participant will complete the *Form 44. Health History Form* in RedCap
3. Research Project coordinator will educate participant on CaD referencing *Form 45. Instructions for Calcium and Vitamin D Usage* and using *Protocol 42. Administering Edu CaD* as a guide.
4. Participant will complete the *Form 46. Goal Setting CaD form*, *Form 47. Task & Barrier Calcium* and *Form 48. Task & Barrier VitD* form in RedCap
5. RPC will prescribe calcium and vitamin D on the *Form 49. Calcium and Vitamin D Prescription Sheet* using *Protocol 41. Prescribing Calcium and Vitamin D*. RPC will educate participant on usage of the cards using *Form 1. Calendar Card Instructions* document.
6. Participants to be educated on mail back procedure and given SASE for convenience.

Risedronate Group:

1. Participant Manual will contain the same documents as the Participant Manual Control plus the following:
 - a. *Form 50. Instructions for Taking Your Risedronate*
 - b. *Form 51. Lexicomp Online Patient Education Risedronate*
7. Participant will complete *Form 43. NOF Calcium Intake Estimate_Revised* using paper and pencil (see *Protocol 40. NOF Calcium Intake Calculator*)
8. Participant will complete the *Health History Form* in RedCap
2. Research Project coordinator will educate participant on CaD using *Form 45. Instructions for Calcium and Vitamin D Usage* as a guide (see *Protocol 42. Administering Edu CaD*)
3. RPC will educate participant on Risedronate using *Form 50. Instructions for Taking Your Risedronate* as a guide (see *Protocol 43. Administering Edu Risedronate*).
4. Participant will complete the *Form 46. Goal Setting CaD form*, *Form 52. Goal Setting Risedronate* form, *Form 47. Task & Barrier Calcium* form, *Form 48. Task & Barrier VitD* form, and *Form 53. Task & Barrier Risedronate* form in RedCap
5. RPC will prescribe calcium and vitamin D using forms and protocols referenced under “Control Group Protocol”, #6.
6. Participants to be educated on mail back procedure and given SASE for convenience

Exercise Group Protocol:

1. Participant Manual will contain the same documents as the Participant Manual Control plus the following:
 - a. *Form 54. YMCA Membership Application*
 - b. *Form 10. YMCA Contact Sheet for Participants_Version 3*
2. Participant will complete *Form 43. NOF Calcium Intake Estimate_Revised* using paper and pencil (see *Protocol 40. NOF Calcium Intake Calculator*)
3. Participant will complete the *Form 44. Health History Form* in RedCap
4. Research Project coordinator will educate participant on CaD using *Form 45. Instructions for Calcium and Vitamin D Usage* as a guide (see *Protocol 42. Administering Edu CaD*)
5. Participant will complete the *Form 46. Goal Setting CaD form*, *Form 47. Task & Barrier Calcium* and *Form 48. Task & Barrier VitD* form in RedCap
6. Participant will complete the *Form 54. YMCA Membership Application* and be introduced to Exercise program. Use *Protocol 44. Steps to Take After Randomization to Exercise Group* as a guide.
7. RPC will prescribe calcium and vitamin D using forms and protocols referenced under “Control Group Protocol”, #6.
8. Participants to be educated on mail back procedure and given SASE for convenience.

Note: During week 2, RPC will complete the following instruments with the participant: 1. *Form 55. Goal Setting Exercise*, 2. *Form 56. Task and Barrier Exercise*, and 3. *Form 57. Barriers Interference Instrument*, and the following educational materials: 1. *Form 58. Reminder List for Exercises*, 2. *Form 59. Signs and Symptoms*, 3. *Form 60. Sore vs. Pain*, 4. *Form 61. Know the Facts About High BP*, 5. *Form 62. HOPS Posture*

7. RPC will fill out *Form 63. Payment Info Form*. If personnel ID is unknown, ask participant to send via email or verify over the phone.
8. RPC will give all participants a chance to ask any questions and ensure they understand the process of the study. RPC will remind participant that they will contact the participant in two weeks.

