Description of Intervention:	
This proposed study has a randomized 3-group (2 treatment groups & 1 control group), repeated measures experimental design. A computer generated code will be used to stratify subjects by exercise at baseline and then randomized to 3 groups (Control: n =103; Risedronate: n =103; Exercise: n =103) with assignments placed in sealed opaque envelopes for sequential use. All subjects will take dosages of calcium citrate supplements sufficient to ensure their total daily calcium (diet+supplements) is ~ 1200 mg daily and vitamin D³ supplements with daily dose to ensure serum levels of vitamin D [25 (OH)D] are between 30 ng/mL and 80 ng/mL(optimal CaD). Subjects randomized to the Risedronate group will take optimal CaD daily and 150mg of oral risedronate once monthly for 12 months but will not participate in the exercise program. Subjects randomized to the Exercise group will take optimal CaD and also participate in 12 months of a bone-loading exercise program three times weekly at a local community-based YMCA (Y). To ensure the bone outcomes were not due to the CaD supplementation, a group taking only optimal CaD will serve as a control. While only women in the exercise group will participate in the structured bone-loading exercise program developed for this study, all women will be encouraged to participate in exercises and will be informed of the benefit of weight bearing and resistance exercises. The primary outcome will be bone structure at the tibia and hip and secondary outcomes are bone mineral density (BMD) and bone turnover. Repeated measures of primary and secondary outcome variables will be conducted at baseline, 6 and 12 months to better understand response to intervention components with a

	maximum difference expected at 12 months. An exercise intervention lasting 12 months or 2 to 3 bone turnover (resorption / formation) cycles is necessary in order to measure the effects of training on bone outcomes.
Study Duration:	Time from subject enrollment to completion of analysis is 4 years and 6 months.
Subject Participation Duration:	Each subject will be asked to participate in the study for a total of 12 months.
Estimated Time to Complete Enrollment:	Study enrollment will begin in Year 1, month 6 and continue through Year 4, month 9.

SCHEMATIC OF STUDY DESIGN:

See [Protocol 1. Timeline for Data Collection](#), for details regarding collection of specific measures

Prior to
Enrollment

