5.3 Treatment Assignment Procedures

A computer generated code will be used for randomization to 3 groups (Control: n =103; Risedronate: n =103; Exercise: n =103) with assignments placed in sealed opaque envelopes for sequential use.

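### Section 6.4.4 takes each allocation from the top of a desk pile of sealed envelopes, and the visible text describes nothing that would show the order was kept

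*Combined protocol and SAP*

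**What the plan says.** Section 5.3 specifies a computer-generated code for three groups of 103, "with assignments placed in sealed opaque envelopes for sequential use". Section 4 repeats this and calls the design stratified. The Protocol Summary (Description of Intervention) names the factor: "A computer generated code will be used to stratify subjects by exercise at baseline and then randomized to 3 groups". Section 5.3 mentions no strata.

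Section 6.4.4 gives the order of the enrollment visit:

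1. Main-study consent is completed.
2. The next envelope is taken from the top of a "pile located in desk in HOPS office at ORC) and read treatment group out loud".
3. The checklist for that arm is chosen (Forms 35 to 37).
4. The calcium intake form is filled in.
5. The woman goes for her pQCT scan.
6. While she is being scanned, the first instruction is "Open RedCap complete the ID# assignment using" Protocol 24.

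She is already known to the study by then. At the screening visit (6.4.2) staff "look in Screening Binder to identify the individual's ID# and assigned RPC", and "personnel should open RedCap on the Ipad and assign an ID# according to the" same protocol.

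**The concern.** Envelope allocation protects against selection only if each envelope is committed to a particular woman before it is opened, and if the order can be checked afterwards. Here the only stated rule for which envelope comes next is its position in a pile. A pile can be disturbed, by accident or on purpose, and leave no mark.

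The arms give people reasons to care which envelope comes up. One asks for three gym sessions a week for 12 months, one for a monthly drug, and one for supplements only, and the arm is announced at the visit. If assignments were steered, the Exercise comparisons under Aim 1 would no longer rest on randomization alone. Section 5.4.2 promises follow-up of off-protocol women under intent-to-treat principles. That promise can be verified only against a list of randomized women and arms that was fixed at the moment of allocation.

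**Working it through.** No figure in the plan bears on this point, so the check is a comparison of the stated steps. The sample size was reproduced only to confirm that it is not involved. Inputs from 10.2 are f = 0.10, alpha = 0.05, 3 time points, correlation 0.5 and two groups. With λ = f²·N·m/(1−ρ), N = 164 gives λ = 0.01 × 164 × 3 / 0.5 = 9.84 on 2 and 324 df, and power 0.805. N = 162 gives 0.7998, just short. Then 164 × 1.5 = 246, and 82/0.8 = 102.5, rounded up to 103 per group, or 309. The stated figures hold and do not change.

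**What each existing record can show**

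| Record | Where and when | Shows | Does not show |
|---|---|---|---|
| Screening ID# (binder and REDCap) | 6.4.2, before eligibility is settled | The woman was screened | That she was randomized, or with which envelope |
| Main-study consent | 6.4.4 step 1, before opening | She agreed to take part | Which envelope was next |
| Arm-specific checklist | 6.4.4 step 3, after opening | The arm she was recorded in | That this was the arm due in sequence |
| REDCap ID# step | 6.4.4 step 6, after opening | An enrollment entry was made | Anything about the envelope |
| RPC and RET audits, at least every 3 months | 9 | Compliance with intervention and testing procedures | Allocation sequence not named |
| DSMC audit, every 6 months | 9 | Consent, eligibility, accrual, violations, withdrawals | Envelope accounting not named |

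**Three possible departures**

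- *A woman leaves on hearing her arm.* Her signed consent would have no completed checklist or follow-up beside it, so she could be traced. Her tibial baseline would be missing, because the pQCT is step 5.
- *An envelope is set aside and the next one used.* The checklist records the arm actually given. With unnumbered envelopes, nothing described in the text shows that one was passed over.
- *Two envelopes change places.* Both women have a consent and a checklist, and each record looks complete.

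Listing recorded arms in order of consent and comparing them with the code would expose some cases of the second and third kind. The protocol does not call for that comparison. Without envelope numbers and times of opening, a mismatch would be hard to interpret.

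**Could a procedure elsewhere fill the gap?** In 6.4.4, steps 1, 3, 4 and 6 each cite a form or protocol; step 2 cites none. Among the 50 protocols and 64 forms listed by title in the appendices, none is a randomization procedure or an allocation log. Protocol 44 starts after randomization to Exercise.

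**Stratification.** The Protocol Summary stratifies by baseline exercise, while 6.4.4 describes one pile. A single pile opened from the top cannot deliver a separate sequence for each stratum. Either there is one pile per stratum and 6.4.4 omits it, or the stratification is not carried out as described.

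**The case against.** The strongest reply is that sealed, opaque envelopes used in sequence from a computer-generated code are a recognized method, and the protocol states all of those features. Setting an opened assignment aside or shuffling the pile would break the written rule; nothing in the plan permits it. The woman has an ID# from screening, her consent is signed before the envelope is opened, and an arm-specific checklist follows at once. Audits run at two levels. Protocols 24, 39 and 45 and Forms 35 to 37 are visible by title only, and record keeping is deferred to the IRB Application. Any of these could contain a recording step.

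Much of this stands, and it rules out several stronger readings that a reader might infer:

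- *That allocations can go unrecorded with no audit trail.* The consent, ID# and checklist are a trail of who consented and which arm was recorded, and the unseen documents may hold more.
- *That the late REDCap step leaves the woman unidentified at allocation.* She already has a screening ID#. Moving that step earlier would not by itself keep the pile in order.
- *That nobody at the visit is masked.* Section 6.1 says assessors of the outcomes are blinded, and the baseline pQCT is done at this visit.
- *That the staff who enroll a woman open her envelope.* This is likely, but step 2 names no one.
- *That allocations were in fact steered.* Nothing in the documents suggests it.

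The reply does not supply any described means of showing that the sequence was followed.

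**Conclusion.** The point holds as a gap in verifiability. As described, the procedure could be followed faithfully and still not be shown to have been; a departure from sequence might not be detected. The conclusion rests on the visible text and would weaken if an allocation log or numbered envelopes are specified in a document known here only by title. In that case step 2 should cite it.

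The size of any bias cannot be estimated. The shift in an arm's mean would be roughly the fraction of assignments diverted times the difference in outcome between the women diverted and the rest, and the documents give neither. The mismatch between stated stratification and a single pile needs no such assumption and should be reconciled in any case. The case for change is that a more bias-resistant step is available cheaply, using a system the visit already opens.

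**What to change.** In 5.3 and 6.4.4, put registration before allocation. Record in REDCap the ID, date and time, confirmed eligibility and baseline-exercise stratum, then have REDCap release the computer-generated assignment for that stratum. State how the stratum is defined; activity questionnaires (Forms 24 and 25) are already completed at screening, so the information can be available in time.

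If envelopes are kept, number them serially within stratum. Write the ID and date-time on the sealed envelope before it is opened. Reconcile used and unused envelopes against the code list in each six-monthly DSMC report.

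The cost is a few hours of database set-up and one changed step in the visit. The downside of the REDCap route is that allocation then depends on the connection, which the visit already needs. Sample size and analysis do not change.
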